13.4 Primary Objective, Endpoint(s), Analysis Plan

The primary objective of this study is to determine the safety and toxicity of topical 1% bexarotene gel application to the breasts of healthy women at high risk for breast cancer for a duration of 4 weeks. Women with ADH, ALH, LCIS, breast cancer survivors (DCIS or invasive) ≥ 5 years from their diagnosis, BRCA 1/2 mutation carriers, and women with elevated risk for breast cancer $\geq 1.7\%$ in 5 years or lifetime risk $\geq 20\%$ will be recruited. Three dose levels are considered (10mg every other day, 10mg daily, and 20mg daily). Dose Limiting Toxicity (DLT) is defined as a grade 2 skin adverse event that persists for at least 6 days or any grade 3 or greater adverse event possibly, probably, definitely related to the study drug. In addition, a DLT will be a grade 2 skin adverse event that recurs and persists for at least 3 days. A conservative modification of the standard “3+3” design will be applied. The first cohort of 3 participants will be treated at the first dose level (10mg every other day). New cohort of participants will not be treated until toxicity has been fully evaluated for all current participants for 4 weeks. We will add another 4 participants when only 1 or less participants experience DLT in 6 treated participants. We will only escalate dose to the next higher level when 20% or less of total participants experience DLT. At any dose level, the algorithm is as follows:

- (1) If 0 or 1 out of 3 participants experience DLTs ($\leq 1/3$), an additional cohort of 3 participants will be treated at the same dose level. If total number of participants experiencing DLT at that dose level is 1 or less out of 6 ($\leq 1/6$), we will enroll another 4 participants the same dose level.
- (2) If at any time 2 or more participants experiences DLTs in 3 or 6 participants ($\geq 2/3$ or $\geq 2/6$) or 3 or more participants experience DLT in 10 participants ($\geq 3/10$), then the dose escalation will stop, and the next lower dose will be considered as the maximum tolerated dose (MTD).
- (3) In 10 participants at each dose level, if we observe 2 or less DLTs, a cohort of 3 participants will be treated at the next higher level. If 3 or more in 10 participants experience DLT, we will stop accrual to that level and above, and claim the regimen as to be too toxic for that level or above.

MTD is defined the highest dose level with at most 2 participants with DLTs in 10 participants treated.

Once MTD is identified, we will enroll another 10 participants into MTD and these participants will have mandatory biopsies before and after 4 weeks of treatment. We will continuously monitor aggregate DLTs in these participants together with the 10 participants treated during the dose escalation part of the study. If at any time the posterior probability of observing a DLT rate of at least 20% exceeds 70%, i.e., $\Pr(\text{DLT rate} \geq 0.20 \mid \text{Data}) > 70\%$, given the prior of the DLT rate of beta (0.2, 0.8), we will stop the trial and claim the dose is too toxic. Given the above rule the boundaries for early stopping due to excessive DLT are Total Number of Participants with DLTs/Total Number of Participants $\geq 4/11\sim 14$, $5/15\sim 19$, and $6/20$. Combining with the boundaries during dose escalation phase, i.e., stop accrual at the dose level if Total Number of Participants with DLTs/Total Number of Participants $\geq 2/3$, $2/6$, $3/10$, $4/11\sim 14$, $5/15\sim 19$, and $6/20$, the early stopping probability for this level will be 15%, 51%, 82% if the true DLT rate is 0.10, 0.20, and 0.30, respectively.

Given that there are 3 dose levels and 10 participants enrolled and treated at each level, and 10 additional patients at MTD, it is anticipated that 40 participants will be treated and up to 40 will be evaluable at the end of this study.

At the end of the study, the toxicity data will be summarized for each dose level using frequency tabulation. The compliance of treatment application for each dose level will be presented using descriptive statistics.

13.5 Secondary Objectives, Endpoints, Analysis Plans

Secondary Objectives:

1. To detect bexarotene concentration in the serum at baseline and at 4 weeks of treatment.
2. To detect bexarotene concentration in the breast tissue at 4 weeks of treatment in the dose escalation group.
3. To investigate the effects of topical bexarotene on serum biomarkers
We will determine the change from the baseline in:
 - i. Lipid Biomarkers (Total Cholesterol, triglycerides, LDL, HDL)
 - ii. Thyroid Function Biomarkers (Thyroid Stimulating Hormone (TSH), T4, T3)
 - iii. Calcium

These measurements will be summarized using mean, standard deviation and median (range) for continuous variables at each time point. Wilcoxon rank-sum test may be used to examine the difference of continuous variables between participants' characteristics groups. Participants' demographic characteristics will be compared between different dose levels by Wilcoxon rank-sum and Fisher's exact test for continuous and categorical variables, respectively. In order to explore the changes over time, values of bexarotene concentration and biomarkers in serum will be plotted as functions of time (baseline, week 1, week 2, and week 4). Linear mixed effect model will be applied to model the biomarker change over time for all participants. Appropriate transformation and regression model will be used to ensure the model fit. Estimated bexarotene concentration mean in the breast tissue at 4 weeks will be calculated along with a 95% confidence interval. Other statistical methods may be applied when appropriate.

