1.2 Secondary Objectives

1. To detect bexarotene concentration in the serum at baseline and at 4 weeks of treatment.
2. To detect bexarotene concentration in the breast tissue at 4 weeks of treatment in the dose escalation group.
3. To investigate the effects of topical bexarotene on serum biomarkers we will determine the change from the baseline in:
 - i. Lipid Biomarkers (Total Cholesterol, triglycerides, LDL, HDL)
 - ii. Thyroid Function Biomarkers (Thyroid Stimulating Hormone (TSH), T4, T3)
 - iii. Calcium

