 - If a pregnancy is discovered after Day 0, instruct the participant to stop applying the gel, take participant off-study, complete the Off-Study CRF, follow the pregnancy to term and complete the Outcome of Pregnancy CRF.
- d) Research blood sample for serum bexarotene level.
- e) Participants need to have had any breast imaging with a normal/benign (bi-rads 1 or 2) result within 180 days of Day 0 and no further routine breast imaging planned during the course of the study (4 weeks). Exception: if the mammogram result was a bi-rads 0 and the imaging work-up (ultrasound and/or MRI) result comes back normal/benign (bi-rads 1 or 2) before treatment initiation, then participant is eligible.
- f) Participants must be instructed to apply the last dose of their study medication on the last day of the study (Day 28).
- g) Dermatology evaluation within 72 hours of study visit if participant experiences a grade 3 skin event or continues to have a persistent grade 2 skin event despite dose modification.
- h) The core biopsy at Day 28 is optional for dose escalation cohort participants. The biopsy is mandatory for participants in the dose expansion cohort at Day 28. If the participant is on aspirin, non-steroidal anti-inflammatory drugs or Vitamin E, she will be instructed to discontinue these 7 days prior to the end of treatment biopsy.
- i) See Appendix D “Alcohol and Tobacco Use Assessment Questionnaires – Baseline”.
- j) See Appendix E “Alcohol and Tobacco Use Assessment Questionnaires – Follow Up”.

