- Participants need to have had any breast imaging with a normal/benign (bi-rads 1 or 2) result within 180 days of Day 0 and no further routine breast imaging planned during the course of the study (4 weeks). Exception: if the mammogram result was a bi-rads 0 and the imaging work-up (ultrasound and/or MRI) result comes back normal/benign (bi-rads 1 or 2) before treatment initiation, then participant is eligible.
 - Tobacco and Alcohol Use Assessment, using the Baseline questionnaires. See Appendix D “Alcohol and Tobacco Use Assessment Questionnaires – Baseline”. Refer to Appendix F for resources for alcohol and tobacco quitting. These resources can be given to individuals if there is concern about alcohol or tobacco dependence. It is not expected that investigators will refer individuals for assistance or that they will undertake the care of individuals for alcohol or tobacco dependence.
 - Confirm eligibility: At the completion of the screening period, eligibility must be confirmed. Only after eligibility is confirmed, eligible participants can be assigned to a dose level and scheduled for the on study tests and procedures.

Day 0

The following procedures will be conducted on Day 0:

- For women of childbearing potential a pregnancy test must be completed within 72 hours prior to or on Day 0. Either a serum or urine pregnancy test may be performed. If a urine pregnancy test is performed, the test must be done in the clinic or in the lab:
 - If pregnancy test result is positive on Day 0, do not dispense drug, take participant off-study, complete the Off-Study Case Report Form (CRF), follow the pregnancy to term and complete the Outcome of Pregnancy Case Report Form (CRF).
 - If a pregnancy is discovered after Day 0, instruct the participant to stop taking drug, take participant off-study, complete the Off-Study CRF, follow the pregnancy to term and complete the Outcome of Pregnancy CRF.
 - Study drug should be initiated on the second or third day of a normal menstrual period.
- Research Blood Sample for serum bexarotene concentration.
-
- Depending on the dose assignment, participants will receive:
 - Bexarotene 1 % gel 10mg/breast/every other day x 4 weeks
 - Bexarotene 1% gel 10mg/breast/daily x 4 weeks
 - Bexarotene 1% gel 20mg/breast/daily x 4 weeks
- Review guidelines for gel application with the participant.
- Review Gel Diary with the participant (see Appendix C). Provide instructions on use of diary.

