7.3 Evaluation During Study Intervention

Day 1

- Participants will initiate study agent on Day 1.

Day 8 \pm 2 days: Phone Call

- Participants will receive a phone call from the PI or designee for an assessment of adverse events. To assess skin toxicity please ask the participant non-leading questions such as “Have you noted any changes in the skin of your breast?” If the participant reports yes, then utilize the plain language guide (Appendix G) to ask more probing questions as needed. Refer to Table 3 for modified CTCAE for assessing skin toxicity of bexarotene gel applied to the breast skin.
- Gel diary will be reviewed.

Day 15 \pm 2 days

- Participants will return for an assessment of adverse events and breast exam. To assess skin toxicity please ask the participant non-leading questions such as “Have you noted any changes in the skin of your breast?” If the participant reports yes, then utilize the plain language guide (Appendix G) to ask more probing questions as needed. Refer to Table 3 for modified CTCAE for assessing skin toxicity of bexarotene gel applied to the breast skin. Gel diary will be reviewed. Vital signs will be measured. Routine blood sample will be obtained during the visit to evaluate for systemic toxicity.
- All skin AEs will be photographed by medical photography services.
- If Grade 3 adverse event is noted on exam, drug will be held and participant will be evaluated by dermatology within 72 hours of the study visit.

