7.4 Evaluation at Completion of Study Intervention

Day 28 \pm 2 days

- Participants will return for an assessment of adverse events and breast exam. To assess skin toxicity please ask the participant non-leading questions such as “Have you noted any changes in the skin of your breast?” If the participant reports yes, then utilize the plain language guide (Appendix G) to ask more probing questions as needed. Refer to Table 3 for modified CTCAE for assessing skin toxicity of bexarotene gel applied to the breast skin. Medical history and concomitant medications will be reviewed. Gel diary will be reviewed and collected. Routine and research blood samples will be obtained during the visit. Pregnancy test will be repeated at this visit. The breast core biopsy will be scheduled at this visit for those participants in the dose escalation cohort who opt for the procedure and for all participants in the dose expansion cohort. Breast tissue will be evaluated for bexarotene concentration. Remaining study drug will be collected at this visit.
- Vital signs will be measured. Weight will be recorded.
- All skin AEs will be photographed by medical photography services.
- If Grade 3 adverse event is noted on exam, participant will be evaluated by dermatology within 72 hours of the study visit.

- Tobacco and Alcohol use assessment will be performed on Day 28, using the “Alcohol and Tobacco Use Assessment Questionnaires – Follow Up” questionnaires (see Appendix E).

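### Does it matter that section 13.5 plots serum values at weeks when the schedule draws no matching blood sample?

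*Combined protocol and SAP*

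**What the plan says.** The analysis text in section 13.5 gives one list of plot times for bexarotene and the serum biomarkers together: "values of bexarotene concentration and biomarkers in serum will be plotted as functions of time (baseline, week 1, week 2, and week 4"). The same section says: "These measurements will be summarized using mean, standard deviation and median (range) for continuous variables at each time point". It also plans a linear mixed model for biomarker change over time and leaves room for other methods where appropriate.

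The sampling text is spread over several sections:

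- Objective 1 in section 1.2, repeated in 13.5: "To detect bexarotene concentration in the serum at baseline and at 4 weeks of treatment".
- Section 7.1, footnote d, defines the research sample: "Research blood sample for serum bexarotene level". The table marks that row at Day 0 and Day 28 only.
- Section 7.2, Day 0: "Research Blood Sample for serum bexarotene concentration".
- Section 7.3, Day 8: "Participants will receive a phone call from the PI or designee for an assessment of adverse events".
- Section 7.3, Day 15: "Routine blood sample will be obtained during the visit to evaluate for systemic toxicity".
- Section 7.4, Day 28: "Routine and research blood samples will be obtained during the visit".

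Section 8.2.1 places the lipid, thyroid and calcium measurements at baseline, Day 15 and Day 28. Section 10.2 lists draws at those same three visits for bexarotene and biomarkers together, without dividing the analytes by visit. It collects lithium-heparin tubes and stores plasma. The Part 1 schema gives serum bexarotene at Day 0 and Day 28; the Part 2 schema mentions Day 28 alone.

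**The concern.** An analysis plan that names time points with no data behind them suggests one of two things. Either the plan expects samples that the clinic was never told to draw, or the list was not brought into line with the schedule. If the first were true, the profile of bexarotene over time would lose half of its intended points, and the samples could not be recovered later.

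Three neighbouring points add to the impression. The Part 2 schema omits Day 0 for serum bexarotene, and a missed pre-dose sample cannot be replaced once treatment has begun. The objectives speak of serum while section 10.2 handles plasma. Section 13.5 also summarises bexarotene by mean and standard deviation, although section 6.1 describes levels after topical use as sporadic and low. No rule says how values below the assay limit enter those summaries, and no proportion quantifiable is listed.

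At stake is the description of systemic exposure. This matters to the trial's rationale in section 2.3, which hopes for breast penetration without high systemic levels.

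**Working it through.** The plan gives no numerical figure to reproduce on this point, so the check sets the listed times against the scheduled samples.

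| Time in 13.5 | Visit in 7.1 | Biomarkers scheduled? | Bexarotene scheduled? |
|---|---|---|---|
| Baseline | Baseline / Day 0 | Yes | Yes (Day 0) |
| Week 1 | Day 8, telephone | No | No |
| Week 2 | Day 15 | Yes | No under 7.1 to 7.4; open under 10.2 alone |
| Week 4 | Day 28 | Yes | Yes |

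Biomarkers: 4 listed, 3 scheduled, so 4 − 3 = 1 has no sample. Bexarotene: 4 listed, 2 scheduled, so 4 − 2 = 2 have none; if section 10.2 is taken to include a Day 15 bexarotene tube, 4 − 3 = 1.

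**Could a conditional sample fill week 1?** Section 5.5 adds lipid monitoring after grade 1 hypertriglyceridaemia and names Day 22 for the extra specimen. The first scheduled on-treatment laboratory tests are at Day 15. This gives no scheduled week 1 value and no bexarotene value at any time.

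**What would a wrong time label change?** The plot can show only observed values. The mixed model for the biomarkers can be fitted to three scheduled times, and section 13.6 says that available data from other time points enter the repeated-measures analysis. For bexarotene, the profile becomes a comparison of Day 0 with Day 28, which is what objective 1 asks for.

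**Is the Day 0 sample at risk in the expansion group?** The Part 2 schema leaves it out, but sections 7.1 and 7.2 apply to all participants, and section 3 gives the expansion group the same schedule of events as the escalation group. The detailed text is therefore consistent. Little is expected at Day 0 in any case, because section 4.2.10 excludes retinoid use within the last 30 days.

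**Is collection unclear because of the matrix name?** No. Section 10.2 fixes the tube, the spin and the plasma aliquots, and the published levels quoted in section 6.1 are also plasma levels.

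**How much could values below the assay limit matter?** The documents state no limit, so this is an illustration on assumed inputs, not an estimate for this trial. With n values, k of them quantifiable, and limit L, setting the low values to L instead of zero moves the mean by ((n − k)/n) × L. Take n = 20 (10 treated at the maximum tolerated dose in escalation plus 10 in expansion), and assume k = 5, each at 3 ng/mL, with L = 1 ng/mL. Setting the low values to s gives a mean of (5 × 3 + 15 × s)/20:

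- s = 0: 15/20 = 0.75, SD 1.33
- s = 0.5: 22.5/20 = 1.125, SD 1.11
- s = 1: 30/20 = 1.50, SD 0.89

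The gap of 1.50 − 0.75 = 0.75 equals (15/20) × 1. The median is below the limit and the proportion quantifiable is 5/20 = 25% in all three cases. In this example the mean and SD depend on convention, while the median that section 13.5 already plans does not.

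**The case for a change.** The strongest argument for a change concerns low values. Objective 1 is about detection, yet the listed summaries are those of a well-measured continuous variable. At baseline most values should fall below any reasonable limit, so their mean and SD would largely reflect an unstated convention. Stating the limit and reporting the proportion quantifiable would cost one table line and no added visit, sample or assay.

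That would be good practice, and an analyst would be expected to do it. It remains an optional addition and corrects no error. Section 8.2.2 refers to an assay developed and qualified for this study, and a quantification limit normally sits in that method's documentation. Section 13.5 already includes the median and range and permits further methods. Any size put on the effect rests on an assumed limit, an assumed count and assumed values.

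A breakdown by dose level with exact intervals would add little at the second level. Section 3 reports that four participants were enrolled there and one withdrew. With none quantifiable, the exact 95% interval has upper bound 1 − 0.025^(1/n), which is 71% for n = 3 and 60% for n = 4.

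On the time points, one can argue that sections 10.2 and 13.5 together reveal an intention to measure bexarotene at Day 15. That reading cannot be ruled out from 10.2 alone. Against it stand the 7.1 table, the contrast between routine blood at Day 15 and routine plus research blood at Day 28, the Part 1 schema, and the objective restated in 13.5 itself. Under either reading, the analyst plots whatever samples exist.

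**Conclusion.** The inconsistency is genuine and clerical. The week 1 label has no scheduled sample behind it for any analyte. The week 2 label has none for bexarotene under sections 7.1 to 7.4, with section 10.2 ambiguous. Correcting the labels would alter no result: the plots are exploratory, and the model uses the visits that were sampled. The Part 2 schema line and the serum/plasma wording are settled by the detailed text in sections 3, 7.1, 7.2 and 10.2.

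The treatment of low values is missing detail in a descriptive secondary analysis. Analysts would fill it sensibly by reporting how many values were quantifiable beside the planned median and range. The primary DLT endpoint, the sample size and the stopping boundaries do not use any of these data.

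Section 3 also reports that, as of October 2019, accrual to the first dose level was complete and the second had stopped. Edits to sampling text could therefore now reach only the expansion group, for whom the Day 0 and Day 28 samples are already required. The conclusion assumes that sites follow the section 7 schedule and that the analyst works from the samples actually collected. On that footing the plan can stand as written.

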Rouanet *et al.* evaluated 4-OHT in a pre-surgical trial of 55 postmenopausal women with invasive ER positive breast cancer. Patients applied 4-OHT for 2 to 3 weeks at various dose levels compared to another group receiving oral tamoxifen at 20mg/day. They found that tissue proliferation decreased as measured by Ki-67 levels between baseline and after treatment. There was a significant decrease in proliferation in the topical treatment arms with lower plasma concentrations of tamoxifen compared to oral treatment (12). Lee and colleagues evaluated 4-OHT in women with DCIS for 6 to 10 weeks prior to surgery. Women were randomized to either 4-OHT (4mg/day) or oral tamoxifen (20mg/day) and assessed change in Ki-67 in their DCIS lesions. Tissue concentration of drug was similar between 4-OHT and oral tamoxifen whereas systemic concentrations of 4-OHT were lower than oral tamoxifen. Changes in proliferation were also similar across both arms. No serious adverse events were noted with 4-OHT in this study. Bexarotene is similar to retinoids and thus more likely to have skin reactions than 4-OHT (13).

We hypothesize that topical bexarotene can be applied to the breasts as a chemoprevention agent with penetration to the breast tissue and without having high systemic levels of drug and subsequent side effects and toxicity as seen with oral bexarotene. Data from chemoprevention studies with topical tamoxifen support the concept of topical agents penetrating into the breast tissue and exhibiting biological activity in the tissue. Preclinical models have clearly shown the effect of bexarotene in reducing the incidence of estrogen receptor negative breast cancer. Based on this data, we propose a phase I study to evaluate topical bexarotene in women at elevated risk for developing breast cancer.

Rationale for including Alcohol and Tobacco Assessment Questionnaires

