6. PHARMACEUTICAL INFORMATION

6.1 Bexarotene (*IND #, NCI, Division of Cancer Prevention*)

Targretin® (bexarotene) 1% gel contains bexarotene and is intended for topical application. Bexarotene is a member of a subclass of retinoids that selectively activate retinoid X receptors (RXRs). These retinoid receptors have biologic activity distinct from that of retinoic acid receptors (RARs). The chemical name is 4-[1-(5,6,7,8-tetrahydro-3,5,5,8,8-pentamethyl-2-naphthalenyl)ethenyl] benzoic acid, and the structural formula is as follows:

Bexarotene is an off-white to white powder with a molecular weight of 348.48 and a molecular formula of C₂₄H₂₈O₂. It is insoluble in water and slightly soluble in vegetable oils and ethanol, USP. Bexarotene gel is a clear gelled solution containing 1.0% (w/w) bexarotene in a base of dehydrated alcohol, USP, polyethylene glycol 400, NF, hydroxypropyl cellulose, NF, and butylated hydroxytoluene, NF.

Plasma concentrations of bexarotene were determined during clinical studies in patients with CTCL or following repeated single or multiple-daily dose applications of bexarotene gel 1% for up to 132 weeks. Plasma bexarotene concentrations were generally less than 5 ng/mL and did not exceed 55 ng/mL. However, only two patients with very intense dosing regimens (> 40% BSA lesions and QID dosing) were sampled. Plasma bexarotene concentrations and the frequency of detecting quantifiable plasma bexarotene concentrations increased with increasing percent body surface area treated and increasing quantity of bexarotene gel applied. The sporadically-observed and generally low plasma bexarotene concentrations indicated that, in patients receiving doses of low to moderate intensity, there is a low potential for significant plasma concentrations following repeated application of bexarotene gel. Bexarotene is highly bound (>99%) to plasma proteins. The plasma proteins to which bexarotene binds have not been elucidated, and the ability of bexarotene to displace drugs bound to plasma proteins and the ability of drugs to displace bexarotene binding have not been studied. The uptake of bexarotene by organs or tissues has not been evaluated.

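### Section 13.5 frames the bexarotene objectives as detection but plans no proportion detected and no rule for below-limit values; its one tissue interval is for a mean that may under-cover and may depend on coding

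*Combined protocol and SAP*

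**What the plan says.** Section 13.5 lists the serum objective as "To detect bexarotene concentration in the serum at baseline and at 4 weeks of treatment" and frames the tissue objective for the escalation group in the same way. Section 1.1 B gives tissue concentration at the maximum tolerated dose (MTD) as the aim of the expansion group, in which all 10 women are to have a Day 28 core biopsy (Sections 3 B and 7.6).

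The planned analysis has these parts, all in 13.5:
- Description: "These measurements will be summarized using mean, standard deviation and median (range) for continuous variables at each time point".
- Tissue inference: "Estimated bexarotene concentration mean in the breast tissue at 4 weeks will be calculated along with a 95% confidence interval". The scale of the mean, the type of interval and the set of women are not given.
- A linear mixed model for biomarker change over time, followed by "Appropriate transformation and regression model will be used to ensure the model fit".
- A closing clause: "Other statistical methods may be applied when appropriate".

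Section 8.2.2 names LC-MS/MS as the assay but states no LLOQ. Section 13.6 covers missing data and does not separate a missing value from a below-limit one.

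On expected levels after topical use, Section 6.1 reports "Plasma bexarotene concentrations were generally less than 5 ng/mL and did not exceed 55 ng/mL" and refers to "The sporadically-observed and generally low plasma bexarotene concentrations". It adds that quantifiable results become more frequent as treated area and gel amount rise. Section 6.2 puts the treated area here at about 1% of body surface. For tissue, Section 6.1 says only that uptake has not been studied. Section 2.3 hypothesises a topical agent "with penetration to the breast tissue and without having high systemic levels of drug".

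**The concern.** An objective framed as detection needs a count of women in whom drug was found, with an interval. A mean does not supply it.

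Concentrations have a floor at the LLOQ and are often right-skewed. Values under the floor are known only to be low. If the plan does not say whether they are set to zero, to LLOQ/2, to the LLOQ or left out, the choice is made after the data are seen, and the mean moves with it. For plasma this is foreseeable: levels are sporadic with larger treated areas, and at baseline almost every sample should be below limit because recent retinoid use is excluded (Section 4.2.10).

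Skew alone is a second, separate issue. With about 10 women, a t-interval around an arithmetic mean of skewed data tends to miss on one side, with its upper limit below the true mean.

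At stake is the main result of the expansion cohort: whether drug reaches the breast, how much, and with how much certainty.

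**Working it through.** **Inputs from the documents.** Mandatory biopsies: 10. Optional biopsies among the 10 women already treated at the MTD: 0 to 10, so n is 10 to 20 if pooled. The documents give no SD, CV, LLOQ or target precision for concentration, so there is no figure to reproduce.

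**Assumptions.** Lognormal concentrations with log-SD σ from 0.3 to 1.0. Since CV = √(exp(σ²) − 1), this is a CV of 31%, 53%, 80% and 131% at σ = 0.3, 0.5, 0.7 and 1.0. The mean is read as arithmetic and the interval as mean ± t × SD/√n.

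**Step 1: coverage with every value quantifiable (simulation).**

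| σ | 0.3 | 0.5 | 0.7 | 1.0 |
|---|---|---|---|---|
| Coverage, n = 10 | 94% | 92% | 89% | 84% |

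With n = 20, coverage runs from 94% (σ = 0.3) to 87% (σ = 1.0). Misses are nearly all on one side: at n = 10 and CV 100%, the upper limit lies below the true mean in 12.6% of runs and the lower limit above it in 0.2%.

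**Step 2: dependence of the mean on coding.** Let p be the share below limit and z the standard normal p-quantile.
- Dropping below-limit values multiplies the expected mean by Φ(σ − z)/(1 − p).
- Coding them as zero multiplies it by Φ(σ − z).

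For p = 0.6, z = 0.253:
- σ = 0.3: Φ(0.047) = 0.519. Dropping gives 0.519/0.4 = 1.30 (30% too high); zero gives 0.52 (48% too low).
- σ = 1.0: Φ(0.747) = 0.772. Dropping gives 0.772/0.4 = 1.93 (93% too high); zero gives 0.77 (23% too low).

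Simulated means at CV 100%, n = 10, in LLOQ units:

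| Share below limit | True mean | Coded 0 | LLOQ/2 | LLOQ | Dropped |
|---|---|---|---|---|---|
| 20% | 2.85 | 2.71 | 2.81 | 2.91 | 3.39 |
| 50% | 1.41 | 1.13 | 1.38 | 1.63 | 2.26 |
| 70% | 0.91 | 0.57 | 0.92 | 1.27 | 1.89 |

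The highest-to-lowest spread is 2.26/1.13 = 2.0-fold at 50% and 1.89/0.57 = 3.3-fold at 70%. At 20%, coding matters little unless values are dropped.

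**Step 3: what a detection proportion would give.** Exact (Clopper-Pearson) 95% intervals for 10 women:
- 10/10: lower limit 0.025^(1/10) = 0.69, so 69% to 100%.
- 7/10: 35% to 93%.
- 0/10: upper limit 1 − 0.025^(1/10) = 0.31, so 0% to 31%.

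**Step 4: the log-scale alternative.** With all values quantifiable, the log-scale t-interval covers the geometric mean in 95% of runs. It is wider than the arithmetic interval in only 14% (σ = 1.0) to 35% (σ = 0.3) of runs. Replacing below-limit values by LLOQ/2 before taking logs is not safe: with 60% below limit, coverage is about 67% at σ = 0.3 and 85% at σ = 0.5. A likelihood that treats these values as left-censored avoids that substitution, but it needs at least two quantifiable values. With 60% below limit and n = 10, fewer than two occur with probability 0.6¹⁰ + 10 × 0.4 × 0.6⁹ = 0.006 + 0.040 = 4.6%.

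**The case against.** The strongest replies are these.

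- **Plasma is not tissue.** A reader might infer that tissue levels will often be unquantifiable. The documents do not support this: the statements in Section 6.1 concern plasma, tissue uptake is described as unevaluated, and the trial's hypothesis is that drug does penetrate. This stands. The calculations in Step 2 show what would happen at a given below-limit share; they do not predict the share in tissue.
- **Under-coverage is not established.** A reader might conclude that the interval is too narrow. That depends on a skew the documents do not give. At σ = 0.3 the shortfall is about one percentage point. Only *may under-cover* is justified.
- **Median and range are planned.** True, and useful: with fewer than half the values below limit, the median does not change with substitution at or below the LLOQ. But it carries no interval and does not estimate detection.
- **Transformation and other methods are allowed.** Both clauses are generic. The first follows the mixed-model sentence and is not tied to the tissue mean; neither says what is done with below-limit values.
- **The mixed model.** A reader might think it is to be fitted to bexarotene. Section 13.5 plots bexarotene and the biomarkers together, but describes the model as one for biomarker change, and Section 7.1 schedules bexarotene blood samples only on Day 0 and Day 28. The model need not be dropped.
- **Unlike targets.** The 95% coverage of the log-scale interval is for the geometric mean, so it is not a like-for-like gain over the figures in Step 1. This stands; the fix changes the estimand.
- **Nothing turns on the estimate.** No sample size or stopping rule uses it. That limits the severity, but the expansion cohort has mandatory biopsies for this measurement.

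**Conclusion.** The point holds in limited form and should be fixed. Three things follow from the documents alone: objectives framed as detection have no planned detection proportion, no LLOQ or below-limit rule is stated, and the only tissue inference is a mean with an interval of unstated scale, method and analysis set.

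The size of the effect is conditional on lognormal data. Coverage at n = 10 ranges from 94% down to 84% over σ = 0.3 to 1.0 when all values are quantifiable. Coding matters little at 20% below limit unless values are dropped, and shifts the mean 2- to 3.3-fold at 50% to 70% (CV 100%). Below-limit values are foreseeable in plasma; their share in tissue is unknown. That uncertainty is a reason to fix the rule in advance, not evidence that tissue levels will be low.

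**What to change.** In Section 13.5, for tissue and Day 28 plasma at the MTD:

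1. Report the number and proportion of women with quantifiable drug, with the exact 95% confidence interval.
2. Replace the arithmetic-mean interval with a geometric mean and 95% interval from a lognormal likelihood that treats below-limit values as left-censored. Keep median and range. Use LLOQ/2 as a sensitivity analysis only. With fewer than two quantifiable values, report item 1 alone.
3. State the LLOQ for each matrix, and whether optional escalation biopsies at the MTD are pooled with the 10 mandatory ones. Section 13.8 speaks of women who choose the biopsy and does not settle this.
4. As a descriptive addition, report each woman's Day 28 tissue-to-plasma ratio, as a lower bound (tissue divided by plasma LLOQ) when only plasma is below limit. Give the time between the two samples, since Section 7.4 has the biopsy scheduled at the Day 28 visit and same-day sampling is not assured.
5. Say that the mixed model applies to the lipid, thyroid and calcium biomarkers and not to bexarotene.

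Cost: plan text and a little programming, with no new samples or visits. The estimand changes from arithmetic to geometric mean and must be labelled so; under the lognormal assumption the two differ by a factor exp(σ²/2), which is 1.05 at σ = 0.3 and 1.65 at σ = 1.0. The interval is not generally wider.
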